9.7.1.9 Determination of Sample Size

The sample size and design characteristics to test the hypothesis under the primary objective based on the primary endpoint, the Composite Clinical score at 12 months, were determined by means of simulations. Extensive trial simulations have shown that a total of 800 subjects will be sufficient to demonstrate that the most likely ED₉₀ dose achieves a CSD from placebo with a probability of at least 95% in the IA and greater than 80% in the final analysis if the trial does not stop for early success. There is at least 80% probability of study success for the dose response scenarios where the treatment was considered to have clinically meaningful treatment effect. Simulations have also shown that if there is no efficacy at all for any dose, then the probability of falsely claiming superiority to placebo is no more than 10.0% assuming a 20% dropout rate.

For each of the 6 treatment groups (5 active dose regimens and placebo) the final number of subjects per group will differ depending on the observed interim treatment responses. The simulation plan will be described in the appendix section of the Statistical Analysis Plan, which will present further details.

vMRI

The null hypothesis is that there is no difference between active dose and placebo. There are 5 null hypotheses corresponding to 5 active dose regimens. The alternative hypothesis is that at least 1 null hypothesis is false (1-sided). The null hypotheses will be tested using Dunnett method with 1-sided alpha of 0.05. The statistical power was estimated through simulation for a moderate dose-response assumption that the percent reduction in change from baseline of total hippocampal volume compared to placebo would be 15%, 20%, 25%, 15%, and 20% corresponding to the 5 dose regimens (2.5, 5, and 10 mg/kg biweekly, 5 and 10 mg/kg 4-week interval), respectively. The estimated power for actual planned study sample size is 0.764 at 12 months and 0.694 at 18 months, assuming an attrition rate of 20% at 12 months and an exponential dropout model. Under a stronger dose-response assumption (ie, the percent reduction in change from baseline of total hippocampal volume compared to placebo is twice as much as that in the moderate dose-response assumption), the estimated power is at least 99% at both 12 and 18 months.

AMYLOID PET (IMAGING SUBGROUP)

The null and alternative hypotheses and statistical test are the same as that for vMRI. To estimate the sample size for amyloid PET imaging subgroup at 18 months, a common standard deviation of change from baseline was estimated as 0.4 and a reasonable mean difference between treatment and placebo was estimated as 0.25 (SUVR). The corresponding standard deviation and mean difference at 12 months were estimated as 0.27 and 0.17, respectively. Assuming a moderate dose-response that the best dose regimen would achieve a difference of 0.25 (SUVR), and that the

2 middle and 2 low dose regimens would achieve a difference of 0.2 and 0.15 (SUVR), respectively, it would require a total 230 subjects from all 6 arms at 18 months to achieve an 80% power. This sample size took into account possible unequal number of subjects per arm. Under the same attrition rate assumption as that for vMRI, a total sample size of 306 at 12 months is sufficient to obtain 230 subjects at 18 months. The estimated power with 306 subjects at 12 months is approximately 85%. The postbaseline amyloid PET in the imaging subgroup will be planned for the first 306 subjects who have consented and who are still on treatment at 12 months. (revised per Amendments 02 and 07)

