Annualized rates of change of 2% to 3% have been reported for the AD brain compared to 1% in MCI subjects and <1% in age-matched controls. However, subjects with MCI due to AD – intermediate likelihood (CSF A β <192 or positive amyloid imaging) show rates of atrophy comparable to those observed in Alzheimer’s disease dementia subjects,^{21,22,23,24} supporting the notion that such subjects are on similar trajectories. Lower CSF A β (1-42), amyloid positivity on PET imaging, and higher CSF tau in addition to the presence of the *APOE4* allele have been associated with greater rates of brain atrophy and will be entered as covariates in various proposed analyses.^{25,26} Hippocampal atrophy has been shown to be a significant predictor of clinical progression, independent of amyloid levels in the brain.²⁷ Brain volume (total ventricular volume, whole brain, temporal lobe) generally shows a modest correlation with performance on a number of cognitive scales.^{21,22,23,28} These relationships and the effects of treatment will be further explored. Although it is hypothesized that treatment will be associated with declines in rates of atrophy, worsening atrophy has been described following immunotherapy treatment. Reasons for this paradoxical effect remain unclear but may be possibly related to osmotic shifts or the effects of inflammatory factors produced by activated microglia in response to treatment. To address this issue, baseline brain volumes will be entered in the analysis of volumetric change and consideration will be given to undertaking comprehensive regional analysis, including cortical thickness maps, which may be less susceptible to such effects.

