9.7 STATISTICAL METHODS

All statistical analyses will be performed by the sponsor or designee after the database is locked and released for unblinding. (revised per Amendment 07) At each IA of the primary endpoint, a snapshot of the data will be obtained and released for analysis. A copy of this snapshot will be archived. This process will also be followed for the safety data that will be used for analysis for the DSMB. Statistical analyses will be performed using SAS software or other validated statistical software as required. All statistical tests will be based on the 10% level of significance, except for the Bayesian methods on the primary endpoint (revised per Amendments 09 and 10). Details of the statistical analyses will be included in a separate statistical analysis plan (SAP).

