Statistical methods for the conventional analyses of primary efficacy endpoint will use a mixed effects model with repeated measures (MMRM) comparing placebo to the identified ED₉₀ dose from the Bayesian analysis (revised per Amendment 09). The model will include randomization of stratification variables, clinical subgroup (MCI due to AD, mild AD), the presence or absence of ongoing AD treatment (ie, AChEIs or memantine or both), *APOE4* status (positive, negative), and baseline Composite Clinical Score as covariates. These analyses will be performed on the Full Analysis Set as well as the PP set based on the ITT principle. In case of early success, the conventional analyses will also be performed using the data collected prior to the IA. (revised per Amendment 01)

ANALYSIS OF KEY SECONDARY EFFICACY ENDPOINTS (REVISED PER AMENDMENTS 09 AND 10)

Key Secondary endpoints were ordered to reflect the most recent FDA Draft Guidance and EMA Guideline that prioritizes effects on pathophysiology in early AD, as measured by biomarkers (February, 2018). Conventional analysis will be performed using all available data at the time of success (if applicable), and at 18 months of treatment, regardless of success. An MMRM will be used to compare the combined 10 mg dose group (including biweekly and monthly regimens) with placebo for the key secondary endpoints (revised per Amendments 09 and 10). The rationale for combining the two 10-mg dose regimens is to account for the loss of subjects positive for *APOE4* in the 10 mg/kg biweekly dose group and the inability to randomize *APOE4* carriers to the 10 mg/kg biweekly group following a Regulatory request by European Health Authorities in July, 2014. The key Secondary endpoint based on clinical status (ADCOMS, CDR-SB, and ADAS-Cog) will be analyzed in subjects with EAD as well as separately within subjects with MCI and mild AD dementia. (revised per Amendment 10)

In addition, as sensitivity analysis, MMRM analysis will be performed for the following treatment comparisons: (revised per Amendment 10)

- Combining 2 high doses (10 mg biweekly + 10 mg monthly), 2 middle doses (5 mg biweekly + 5 mg monthly), and the 2.5 mg biweekly dose, resulting in 3 treatment comparisons with placebo (for dose response) (revised per Amendment 10)
- ED₉₀ dose of BAN2401 versus placebo, where the ED₉₀ dose of BAN2401 will be established by Bayesian analysis at 18 months as described in the next paragraph (revised per Amendment 10)

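### The power for hippocampal volume and amyloid PET is stated for a five-dose Dunnett test, but the protocol's planned test is a single combined 10 mg versus placebo MMRM contrast.

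*Protocol*

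**What the plan says.** Section 9.7.1.9, vMRI, sets up the test as follows: "There are 5 null hypotheses corresponding to 5 active dose regimens", and "The null hypotheses will be tested using Dunnett method with 1-sided alpha of 0.05". For the moderate dose-response it gives power of 0.764 at 12 months and 0.694 at 18 months. The amyloid PET part adopts the same set-up: "The null and alternative hypotheses and statistical test are the same as that for vMRI". It gives 80% power with 230 subjects at 18 months and about 85% with 306 at 12 months. The synopsis, Sample Size Rationale, repeats all of this.

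Section 9.7.1.6, for the key secondary endpoints, says: "An MMRM will be used to compare the combined 10 mg dose group (including biweekly and monthly regimens) with placebo for the key secondary endpoints". It lists by-regimen, dose-level, ED90 and top-three-dose comparisons as sensitivity analyses and does not mention Dunnett. The same analysis is extended to the other secondary endpoints. Section 9.7.1.1 makes PET and total hippocampal volume at 18 months key secondary, and both at 12 months secondary.

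Section 9.7 sets the level: "All statistical tests will be based on the 10% level of significance", apart from the Bayesian analysis of the primary endpoint. It does not say one- or two-sided.

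On attrition, Section 9.7.1.9 says that "a total sample size of 306 at 12 months is sufficient to obtain 230 subjects at 18 months", under the volume assumption of 20% loss at 12 months with exponential dropout.

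**The concern.** For the same two endpoints the current text gives two fully specified testing rules. One has five null hypotheses with family-wise control by Dunnett. The other has one null hypothesis on a pooled dose group and needs no adjustment across doses. Both are written as what will be done, so this is not a detail deferred to the SAP.

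The likely cause is visible in the revision history. The sections listed as affected by Amendment 10 include 9.7, 9.7.1.1 and 9.7.1.6, but not 9.7.1.9 or the synopsis sample size text.

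Two things are at stake. A reader of the sample size section would take a Dunnett-adjusted dose-by-dose result as the planned test, while a reader of the efficacy section would take the pooled contrast. And the four stated powers cannot be quoted as the power of the planned analysis.

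**Working it through.** **1. Hypotheses side by side**

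| | Section 9.7.1.9 | Section 9.7.1.6 with 9.7 |
|---|---|---|
| Comparisons | 5 regimens, each versus placebo | combined 10 mg versus placebo |
| Multiplicity across doses | Dunnett | none needed (one contrast) |
| Level | one-sided 0.05 | 10%, sidedness not stated |
| By-regimen results | the test itself | sensitivity analysis |

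The levels can be reconciled: one-sided 0.05 and two-sided 0.10 use the same critical value in the direction of benefit. The first two rows cannot.

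**2. PET at 18 months, 230 subjects**

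Inputs from Section 9.7.1.9: SD 0.4; differences 0.25 (best regimen), 0.20 (two middle) and 0.15 (two low). Following the dose order of the volume assumption, I take 10 mg/kg biweekly as best, and 5 mg/kg biweekly and 10 mg/kg monthly as middle. Allocation in the subgroup is not given, so I use equal arms, 2:1:1:1:1:1, and the arm sizes in Protocol Table 2 (placebo 245; 10 mg biweekly 161; 10 mg monthly 253; total 854).

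Dunnett power is the simulated probability of at least one rejection (critical values 2.24 to 2.29).

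The combined contrast has K = (δ/σ)·√[n0·nc/(n0+nc)] and power Φ(K − 1.645) at two-sided 10%.

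- Equal: n0 = 38.3, nc = 76.7, δ = 0.225; K = 0.5625 × 5.055 = 2.84; power 0.88.
- 2:1: n0 = nc = 65.7, δ = 0.225; K = 0.5625 × 5.732 = 3.22; power 0.94.
- Table 2 shares: n0 = 66.0, nc = 111.5, δ = (161 × 0.25 + 253 × 0.20)/414 = 0.219; K = 0.5486 × 6.438 = 3.53; power 0.97.

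| Allocation | Dunnett, any dose | Combined 10 mg |
|---|---|---|
| Equal | 0.83 | 0.88 |
| 2:1 | 0.90 | 0.94 |
| Table 2 shares | 0.93 | 0.97 |

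Less favourable splits bring the Dunnett figure to between 0.75 and 0.82. The stated 80% is therefore plausible for the Dunnett test but cannot be checked without the allocation.

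**3. Hippocampal volume**

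No mean or SD is given, so 0.764 and 0.694 cannot be reproduced directly. I assumed 800 × 0.80 = 640 at 12 months and 800 × 0.80^1.5 = 572 at 18 months. I then solved for the ratio of placebo change to SD that gives the stated Dunnett powers under reductions of 15, 20, 25, 15 and 20%, and applied that ratio to the combined contrast.

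| Allocation | Ratio, 12 / 18 months | Combined, 12 months (stated 0.764) | Combined, 18 months (stated 0.694) |
|---|---|---|---|
| Equal | 1.37 / 1.33 | 0.83 | 0.77 |
| 2:1 | 1.22 / 1.18 | 0.84 | 0.78 |
| Table 2 shares | 1.16 / 1.13 | 0.86 | 0.81 |

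Example, equal arms at 12 months: n0 = 106.7, nc = 213.3; K = 0.225 × 1.37 × √71.1 = 2.60; Φ(0.955) = 0.83.

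As a check on the back-solving, doubled effects give Dunnett power of at least 0.998, which agrees with the protocol's claim of at least 99%.

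Sidedness matters here. If the 10% level were one-sided, the combined contrast would have about 0.91 to 0.93 at 12 months and 0.87 to 0.89 at 18 months.

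**4. Attrition sentence**

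Retention from 12 to 18 months is 0.80^0.5 = 0.894. So 306 × 0.894 = 274 remain at 18 months, and 230/0.894 = 257.1, so 258 are needed at 12 months. The pair 306 and 230 implies retention of 230/306 = 0.752. The subgroup size of 260 used before Amendment 07 does fit: 260 × 0.894 = 232.6.

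**The case against.** The strongest reply is that the sample size section records how N was justified and need not follow a later change of contrast. Section 9.7.1.6 already names the pooled comparison as the key secondary analysis and labels by-regimen results as sensitivity analyses. The planned contrast has more power than stated, and the Core Study was complete by Amendment 11, so nothing in the design can change. This stands as to consequence: no subject number is affected. It does not remove the contradiction, because Section 9.7.1.9 says what will be tested and does not present Dunnett as a historical sizing basis.

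Four stronger readings are tempting, and the documents do not support them.

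- **Conflicting significance levels.** One-sided 0.05 can be the same test as two-sided 10%. Only the missing sidedness is a fault.
- **A shortfall in the PET subgroup.** The sentence says 306 is sufficient to obtain 230. With about 274 expected, that is true and conservative. The revision history says the subgroup was raised to 306 to increase power, which may explain why it no longer matches the 230.
- **A wrong 85% for PET at 12 months.** Equal arms and proportionally scaled lower-dose effects give 0.92, but the protocol states neither, and says unequal arms were considered. Less favourable splits with the same scaling give 0.86 to 0.91. The 85% cannot be checked; it is not refuted.
- **A test that would miss harm.** Section 7.2.2.2 does say that "worsening atrophy has been described following immunotherapy treatment", and a one-sided test for benefit could not declare it. But the MMRM in Section 9.7.1.6 is not described as one-sided, and Section 7.2.2.2 answers the concern itself by entering baseline volumes and considering regional analyses.

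**Conclusion.** The point holds as an inconsistency and a traceability fault. Section 9.7.1.9 and the synopsis state a five-hypothesis Dunnett test and its power for endpoints that Section 9.7.1.6 tests by one pooled contrast. The figures 0.764, 0.694, 80% and 85% do not describe the planned analysis.

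A reader might infer that the trial was underpowered for these endpoints; the calculation points the other way. On the same allocation the planned contrast gains about 4 to 5 percentage points for PET at 18 months, and roughly 7 to 12 points over the stated figures for volume.

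These sizes rest on a two-sided 10% level, the assumed allocations, the assumed volume totals of 640 and 572, and a cross-sectional approximation to the MMRM with no covariate gain. The conflict between the sections rests on none of these.

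The attrition wording is a minor matter.

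**What to change.** In Section 9.7.1.9 and the synopsis, Sample Size Rationale:

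- Replace the five Dunnett hypotheses with the Section 9.7.1.6 contrast. Alternatively, keep the Dunnett text and mark it as the original sizing basis or as a by-regimen sensitivity analysis.
- Restate power for the combined 10 mg contrast at 12 and 18 months, giving the allocation, the placebo mean and SD for volume, and the 12-month lower-dose PET effects.
- Reword the attrition sentence: 306 at 12 months leaves about 274 at 18 months, 230 would need about 258, and 306 therefore includes a margin.

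In Section 9.7, state whether the 10% level is one- or two-sided.

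Date the correction so that it is not read as prospective, since the Core Study results are already reported in this version. The cost is text and a re-run of existing power code, with no change to enrolment or conduct.

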9.7.2 Interim Analysis

An unblinded independent Interim Monitoring Committee (IMC) will provide oversight to ensure that the response adaptive randomization process and IA perform as expected. An independent data analysis group will perform all of the IA and will provide the results to the IMC.

Randomization to placebo or 1 of 5 dose arms of BAN2401 will be fixed for the first 196 subjects randomized in the study (4:2:2:2:2:2; placebo [4] to each of the active arms [2 each]). After this initial burn-in, adaptive randomization will begin. Randomization probabilities to each arm will be updated at each IA such that the randomization probability will be increased for the placebo arm and arms that represent the potential target dose (ED₉₀), and simultaneously decreased for other active arms. Subjects who are confirmed *APOE4* positive (*APOE4* hetero- or homozygous) will not be randomized to the 10 mg/kg, biweekly dose (revised per Amendments 04 and 05). After each IA, the randomization probability vector will be split between *APOE4*⁺ and *APOE4*⁻ strata to ensure no *APOE4* positive subjects are enrolled on the 10 mg/kg biweekly dose. The overall probabilities as suggested by RAR will still be preserved (revised per Amendments 05 and 07). Details of the estimation of the randomization probabilities will be presented in the Statistical Analysis Plan.

The study will be monitored for early success and early futility (see [definitions in Study Definitions](#)). The first IA will be conducted when 196 subjects are randomized, again when 250 subjects are randomized and again after each additional 50 subjects until 800 subjects are randomized. Sites in Japan will randomize at least 40 Japanese subjects, even if early success is declared or the study achieves 800 subjects randomized. In these circumstances, subjects in Japan will be allocated treatment according to the latest (or last) allocation schedule. If the study reaches its maximum of 800 randomized subjects, additional IA will be conducted every 3 months until all subjects complete 12 months of treatment. Only those subjects who were randomized before the target of 800 was met will contribute to these additional IA, except for the full 12 and 18 month Bayesian analyses. The study will be monitored for futility at each IA and for success starting at the 350 subject IA, until the full 12 months of treatment have been completed. (revised per Amendment 09) Each IA will be conducted on data for the derived Clinical Composite Score. If the efficacy or futility boundary is reached, the IMC will communicate directly with the DSMB members. (revised per Amendment 07)

The study may be stopped for safety reasons at any time.

9.7.3 Other Statistical/Analytical Issues

Not applicable.

9.7.4 Procedure for Revising the Statistical Analysis Plan

If the SAP needs to be revised after the study starts, the sponsor will determine how the revision impacts the study and how the revision should be implemented. The details of the revision will be documented and described in the clinical study report.

11 PROCEDURES AND INSTRUCTIONS (ADMINISTRATIVE PROCEDURES)

11.1 CHANGES TO THE PROTOCOL

Any change to the protocol requires a written protocol amendment or administrative change that must be approved by the sponsor before implementation. Amendments specifically affecting the safety of subjects, the scope of the investigation, or the scientific quality of the study require submission to health or regulatory authorities as well as additional approval by the applicable IRBs/IECs. These requirements should in no way prevent any immediate action from being taken by the investigator, or by the sponsor, in the interest of preserving the safety of all subjects included in the study. If the investigator determines that an immediate change to or deviation from the protocol is necessary for safety reasons to eliminate an immediate hazard to the subjects, the sponsor's medical monitor [and the IRB/IEC for the site must be notified immediately. The sponsor must notify the health or regulatory authority as required per local regulations.

Protocol amendments that affect only administrative aspects of the study may not require submission to health or regulatory authority or the IRB/IEC, but the health or regulatory authority and IRB/IEC (or if regionally required, the head of the medical institution) should be kept informed of such changes as required by local regulations. In these cases, the sponsor may be required to send a letter to the IRB/IEC and the Competent Authorities (or, if regionally required, the head of the medical institution) detailing such changes.

11.2 ADHERENCE TO THE PROTOCOL

The investigator will conduct the study in strict accordance with the protocol (refer to ICH E6, Section 4.5).

11.3 MONITORING PROCEDURES

The sponsor's/CRO's CRA will maintain contact with the investigator and designated staff by telephone, letter, or email between study visits. Monitoring visits to each site will be conducted by the assigned CRA as described in the monitoring plan. The investigator (or if regionally required, the head of the medical institution) will allow the CRO to inspect the clinical, laboratory, and pharmacy facilities to assure compliance with GCP and local regulatory requirements. The eCRFs and subject's corresponding original medical records (source documents) are to be fully available for review by the sponsor's representatives at regular intervals. These reviews verify adherence to study protocol and data accuracy in accordance with local regulations. All records at the site are subject to inspection by the local auditing agency and IRB/IEC review.

In accordance with ICH E6, Section 1.52, source documents include, but are not limited to the following:

- Clinic, office, or hospital charts
- Copies or transcribed health care provider notes which have been certified for accuracy after production
- Recorded data from automated instruments such as IxRS, x-rays, and other imaging reports, (eg, sonograms, computed tomography scans, magnetic resonance images, radioactive images, ECGs, rhythm strips, electroencephalograms, polysomnographs,

pulmonary function tests) regardless of how these images are stored, including microfiche and photographic negatives

- Pain, quality of life, or medical history questionnaires completed by subjects
- Records of telephone contacts
- Diaries or evaluation checklists
- Drug distribution and accountability logs maintained in pharmacies or by research personnel
- Laboratory results and other laboratory test outputs (eg, urine pregnancy test result documentation and urine dip-sticks)
- Correspondence regarding a study subject's treatment between physicians or memoranda sent to the IRBs/IECs
- eCRF components (eg, questionnaires) that are completed directly by subjects and serve as their own source

